Households with at least 1 ARI case during the study period will be included for data analysis. A household with ARI in different years will be treated as 2 different households. Because household visits will be conducted weekly, we will collect specimens for ARI episodes as possible. We will identify these ARI through symptom records. The ARI cases in RSV or *S. pneumoniae* whose dates of onset are within 10 days before or after RSV or *S. pneumoniae* onset will be identified and defined as preceding and subsequent ARI, respectively. We will apply a Bayesian approach to estimate acquisition and clearance rates for RSV or *S. pneumoniae* in a susceptible-infected-susceptible model [37]. The inference relies on repeated measurements of the current status of being a non-carrier (susceptible) or a carrier (infected) of one of the pathogens. We will collect the measurements with sampling intervals. The index cases are the first members of the household to have clinically apparent illness confirmed by laboratory studies. The secondary cases are defined as other family members whose respiratory symptoms occurred later than the index cases' illness. Identified source of infection within the household is defined as the first case in the household who displayed clinically apparent disease and who have clear contact history with individuals outside the household who had illnesses suggestive of *S. pneumoniae* or RSV infection. The infection transmission interval will be defined as the time between the onset of disease for the first case in the household and the onset of disease in a secondary case [38].

Hierarchical generalized linear mixed effect models (HGLMEM)

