In order to assess variables that are significantly impacted in *S. pneumoniae* or RSV infection status across time points in 2 different households, we will fit several random and fixed effects three-level longitudinal generalized hierarchical linear mixed effect models (HGLMEM) with restricted maximum likelihood (REML) estimation method [39, 40]. HGLMEM will be used to evaluate longitudinal *S. pneumoniae* or RSV infection status measurement across time points (level 1) that are nested-within individual subject (level 2) and nested-within household (level 3). Because the model can assume random time effects of measurement, HGLMEM will be a practical strategy for analyzing our data sets. Random effects account for within-subject correlation and will be fitted an unstructured (UN) covariance structure. The structure implies that all different members of a cluster are differently correlated with each other across time. Fixed effects such as the clinical covariates (including clinical data, candidate markers, and target genes), baseline assessment in *S. pneumoniae* or RSV infection status, and household group \times time interaction term will be all included to reflect differential patterns of change over time for the two different household groups. Different fixed effects covariates' combination hierarchical models will be built in the three-level HGLMEM. The HGLMEM will be used to compare the change of *S. pneumoniae* or RSV infection status across time points and to survey the potential associations between these outcomes and independent variables.

Data will be summarized using descriptive statistics. Continuous variables will be expressed as median with interquartile range (IQR) and compared using Mann-Whitney U test. Categorical variables will be presented as frequency and percentage and compared using chi-square or Fisher's exact test, as appropriate. A *P* value less than 0.05 will be considered statistically significant.

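### A secondary case needs only later respiratory symptoms, with no match to the index pathogen or type, so unrelated illness enters the secondary-case count and the transmission interval

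*Combined protocol and SAP*

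**What the plan says.** The Infected model section defines the two ends of a transmission pair in adjacent sentences. For the index case: "The index cases are the first members of the household to have clinically apparent illness confirmed by laboratory studies". For the other end: "The secondary cases are defined as other family members whose respiratory symptoms occurred later than the index" case's illness. The interval follows: "The infection transmission interval will be defined as the time between the onset of disease for the first case in the household" and onset in a secondary case. It therefore takes over whatever the secondary-case definition admits.

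The same section has a 10-day window, for ARI cases "whose dates of onset are within 10 days before or after RSV or" pneumococcal onset. It labels preceding and subsequent ARI and is not tied to secondary cases.

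The information needed for a stricter rule is largely planned. Study design provides swab PCR for pneumococcal serotype and RSV subgroup in symptomatic members, telephone follow-up at 2, 4 and 8 weeks, and repeat laboratory investigation when a member reports symptoms. Family screening by swab and urine is planned when the index illness is lower respiratory. Testing may be incomplete, though: "we will collect specimens for ARI episodes as possible".

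**The concern.** The Significance section gives household transmission as the aim, and the transmission interval is a quantity the plan defines for it. Two pathogens with many types are followed for 24 months, and ARI is identified from symptom records. A later cold in the household need not share the index agent. The written rule counts it anyway, including when the planned swab is negative or shows a different type. Two analysts, one applying the sentence literally and one adding a laboratory requirement, would produce different counts and intervals from the same data.

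A symptom-free contact carrying the index type cannot be a secondary case. That can be a legitimate choice, and isolation rates and the carriage model can still count such a contact if swabbed, but it should be stated.

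**Working it through.** **1. The definitions side by side**

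| Requirement | Index case | Secondary case |
|---|---|---|
| Illness | clinically apparent | respiratory symptoms, later onset |
| Laboratory result | required | not mentioned |
| Same pathogen, serotype or RSV subgroup | not applicable | not mentioned |
| Maximum time from index onset | not applicable | not mentioned |

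No other section supplies the missing entries. The plan states no secondary-case count, attack rate or expected interval, so there is no figure of its own to reproduce.

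**2. Inputs**

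- Windows: 10 days (the ARI rule) and 56 days (the 8-week follow-up). Both stand in the plan; neither is tied to secondary cases.
- Assumed: true attack rate s = 20% (range 10–40%); unrelated respiratory illness r = 2 per person-year (range 1–4), constant and independent of the index illness.

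**3. Share of counted secondary cases that are unrelated**

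Chance of at least one unrelated illness in w days: b = 1 − exp(−r × w/365). Proportion of contacts counted: s + (1 − s)b. Unrelated share: (1 − s)b / [s + (1 − s)b]. This takes all true secondary cases as falling inside the window.

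- 10 days: b = 1 − exp(−20/365) = 5.3%. Counted = 0.2 + 0.8 × 0.0533 = 24.3%. Unrelated = 0.0427/0.2427 = 17.6%. Extremes: 3.9% (s = 40%, r = 1) and 48.3% (s = 10%, r = 4).
- 56 days: b = 1 − exp(−112/365) = 26.4%. Counted = 0.2 + 0.8 × 0.2642 = 41.1%. Unrelated = 0.2114/0.4114 = 51.4%. Extremes: 17.6% and 80.5%.
- No limit, over 24 months: b is 86% at r = 1 and nearly 100% at r = 4, so almost every contact could eventually qualify.

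**4. Effect on the interval**

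The plan's descriptive rule is median and IQR. Contacts were simulated (4 million for the shorter interval, 2 million for the longer), taking the first onset inside the window, with s = 20% and r = 2. True intervals are assumed gamma: mean 5, SD 2.5 days, and mean 14, SD 7 days.

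| True interval | Window | Reported median (range over s and r) | Reported IQR | True pairs outside window |
|---|---|---|---|---|
| Median 4.6, IQR 3.2–6.4 | 10 days | 4.5 (4.4–4.5) | 3.0–6.3 | 4% |
| Median 4.6, IQR 3.2–6.4 | 56 days | 7.6 (5.1–17.5) | 4.1–26.6 | negligible |
| Median 12.9 | 10 days | 6.5 | not needed | 68% |
| Median 12.9 | 56 days | 15.9 (13.5–19.4) | 9.3–28.3 | negligible |

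For the shorter interval at 56 days the reported mean is about 16 days against a true 5. For the longer interval at 10 days the unrelated share rises to about 37%, because most true pairs are cut off. Unrelated here means a contact who was never infected. Counting infected contacts whose first onset was an unrelated illness as well raises the 10-day simulated share for the shorter interval from about 18% to about 20%.

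**The case against.** **Reach.** No declared endpoint rests on the label. The endpoints are isolation rates and serotype, the susceptible-infected-susceptible model uses measured carrier status, and the mixed model uses infection status. This stands and limits the point to the secondary-case label and the interval.

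**Time limits elsewhere.** A household with ARI in different years is treated as two households, follow-up calls end at 8 weeks, and the 10-day rule sits in the same paragraph. These are possible readings, but none is attached to secondary cases, and none adds a pathogen or type match.

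**Size.** Every rate is assumed, and under the only window the plan gives in days, a short interval moves by about 0.1 day. This stands: the larger figures need the 8-week schedule to act as a case window. The result turns on a limit the plan never sets, and even at 10 days unrelated cases stay in the count.

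**The remedy can exclude true cases.** In the preliminary data all 5 subgroup A samples are ON1 and all 8 subgroup B samples are BA9, so genotype there adds nothing to subgroup. The CpsB method returns one best-matching serotype, so a contact carrying several could be called discordant. The planned multiplex PCR for 92 serotypes and a retained symptom-only analysis soften this. It remains a reason to report discordant and test-negative illness visibly.

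**The cited source.** The interval sentence cites an earlier household study that may have confirmed its secondary cases. That cannot be checked here, and the plan's own wording does not require it.

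**Conclusion.** The concern holds and should be fixed. The definition is a wrong rule as written, not merely a missing detail: applied literally, it counts test-negative, type-discordant and unrelated illness as secondary and passes those onsets into the transmission interval.

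The documents do not determine the size. On the stated assumptions the unrelated share is about 18% with a 10-day window and 51% with 8 weeks. The interval is barely distorted at 10 days if true intervals are short, inflated at 8 weeks, and truncated at 10 days if true intervals are long. One borrowed window may therefore not suit both pathogens.

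The isolation-rate endpoint and the two main models are unaffected. Power/Sample Size does not say whether household-acquired infection uses this rule, so no loss of power is claimed.

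**What to change.** **Definition.** Define a secondary case as a symptomatic household member with laboratory detection of the index pathogen, concordant by serotype (S. pneumoniae) or by subgroup/genotype (RSV), with onset inside a pre-specified window for that pathogen. Say whether the 10-day ARI rule applies, and run a sensitivity analysis on the window that includes 10 days. State how adult urine-antigen and swab results combine.

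**Classification.** Treat tested-negative and discordant contacts as non-cases and report them separately. Treat untested contacts as missing and report their number by family type. Keep the symptom-only rule as a sensitivity analysis.

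**Interval.** Compute it only for concordant symptomatic pairs, starting from the laboratory-confirmed index case, and report median and IQR.

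**Asymptomatic contacts.** Report concordant positives separately, only where family screening is planned (lower respiratory index illness).

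**Wording for pneumococcus.** Call matches concordant or probable transmission, and flag known earlier carriage where a baseline result exists. The mixed model lists a baseline assessment of infection status among its fixed effects, but the enrolment row of the Study design table has no specimen, and no routine symptom-free swab is described. A shared serotype may therefore be earlier carriage and does not prove direction.

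**Cost.** SAP wording and classification code, using tests already planned for symptomatic members. The price is fewer secondary cases, possible exclusion of some true ones, missing classifications where no specimen was obtained, and no asymptomatic contact data after an upper respiratory index illness.

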Asymptomatic carriage of *S. pneumoniae* in the nasopharynx is a prerequisite for disease. In the previous study, adults acquire *S. pneumoniae* relatively more in the household than other age groups, and transmissions within household were mostly seen from older to younger siblings [21]. Oropharyngeal colonization is 65.8% of *S. pneumoniae* autolysin (lytA) gene sequence [22]. RSV has become an increasingly documented cause of illness in adults and optimal diagnosis requires reverse transcription polymerase chain reaction (RT-PCR) assays or serology [23].

Close contacts within households may present potential opportunities for RSV transmission [24]. Studies have shown that family members of infants, such as older siblings and parents, are an important RSV infection source in the infants [25, 26]. In about 50% of households, more than one person is infected, and repeat infections in the same individual from homologous or heterologous RSV subtypes within the same season are documented [27]. The identification of RSV infections and increased awareness of the prominent role this respiratory virus has in relatively severe illness in adults by using molecular testing [28, 29]. Besides, the direct interaction between RSV protein and the pneumococcus might result in increased bacterial virulence and worsening disease outcome in respiratory infection [30]. On the other hand, *S. pneumoniae* colonization can enhance subsequent RSV infection [19]. The interactions occurring between *S. pneumoniae* and RSV during respiratory infections and pneumococcal acquisition indicate that pneumococcal serotypes have different ability to cause infection as well as coinfections [31].

[figure not shown]

Significance

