Strategies to prevent these interactions to reduce the incidence of *S. pneumoniae* and RSV infection are very important in children as well as the elderly. The elderly might colonize with *S. pneumoniae* first and then get the RSV acquisition from the younger households. Vaccine delivery should be justified by detailed understanding of *S. pneumoniae* and RSV transmission dynamics. The determinants include carriage rate, age distribution, infection severity, and presence of concurrent *S. pneumoniae* or RSV in the same household. This household-based prospective cohort study aims to establish the household transmission of RSV and *S. pneumoniae* especially in the elderly and infants/children as well as inter-relationship between *S. pneumoniae* and RSV. We hope our data can be utilized in the AI fields to develop a model to predict the transmissions in the exceedingly early stage of disease of *S. pneumoniae* and RSV and strategy of prevention.

Preliminary Data

Our previous data suggest that interactions between RSV and *S. pneumoniae*. RSV infections can increase the ability of adherence of *S. pneumoniae* 15 A in Hep2 cell.

We selected 13 patients for the RSV genotype and 16S ribosomal RNA test. The 16SrRNA revealed *S. pneumoniae* was the predominant bacterial in the nasopharyngeal site.

[figure not shown]
RSV	RSV genotype	16SrRNA
A	ON1	Streptococcus pneumoniae
B	BA9	Streptococcus pneumoniae
A	ON1	Streptococcus pneumoniae
B	BA9	Haemophilus influenzae
A	ON1	Streptococcus salivarius
B	BA9	Streptococcus thermophilus
A	ON1	Streptococcus pneumoniae
B	BA9	Streptococcus lactarius
B	BA9	Streptococcus pneumoniae
A	ON1	Streptococcus pneumoniae
B	BA9	Streptococcus pneumoniae
B	BA9	Propionibacterium acnes
B	BA9	Streptococcus pneumoniae

Study site and population

A **household-based prospective cohort** study will be conducted from 2021 to 2025 in northern Taiwan. We will invite 240 households, having a baby who is discharged from MacKay children's Hospital.

Around 20 babies per months for 12 months adding up to 240 babies in total. The estimation is based on historical discharge number from NBR MacKay Memorial Hospital Taipei. The number is also proved feasible in previous studies.

[figure not shown]
* nuclear family: a couple and their dependent children, regarded as a basic social unit.

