If the households present with **respiratory symptoms**, the visit will be arranged as early as possible. When they presenting to the emergency department, outpatient clinic, or inpatient ward, the urine will be collected for the serotype-specific urinary antigen detection (SSUAD) assays in adult households and the nasopharyngeal or throat swab for PCR will be performed to study serotype of *S. pneumoniae* and RSV subgroup. If the subjects who have clinical syndromes suggestive of pneumonia or bronchopneumonia, they will be asked to participate in the further study along with their household family members. Nasopharyngeal aspiration, urine, blood, and induced sputum will be collected for cultures, PCR and serological test. Clinical manifestations, disease course, and outcomes will be recorded. Family members in the same household will be asked to undergo screening with a nasopharyngeal or throat swab and urine sample. We will trace back 2-week contact history of children in nuclear family who get RSV or pneumococcal infections, especially focus on other family members. The data will be further analyzed to evaluate the influence of short period and long period contact.

Case report form will be used to collect information about the family members, including demographic data, the number of bedrooms in the house, amount of contact time with the patient, presence and pattern of current or recent signs and symptoms and contact history with persons outside of the household who had clinical syndromes suggestive of *S. pneumoniae* or RSV infection.

Follow-up telephone interviews repeated questions about signs and symptoms at 2, 4, and 8 weeks. If any household family member reported experiencing signs or symptoms suggesting *S. pneumoniae* or RSV infection during the follow-up period, clinical assessment and laboratory investigation will be repeated.

	Data collection	Specimen collection
Enrollment	1. information consent form 2. baseline data, including patient demographics, prior medical history, season when discharge, neonatal course and households	
Line follow up period	Checking if there are any respiratory symptoms	
Index case presents symptoms suggesting upper respiratory tract infection		Index case 1. Serotype-specific urinary antigen detection (SSUAD) assays 2. Nasopharyngeal or throat swab for PCR will be performed to study serotype of S. pneumoniae and RSV subgroup. RSV will be sequenced to ascertain F protein heterogeneity.

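### Index case, source, secondary case and transmission interval are all defined by illness, so a symptom-free pneumococcal carrier can hold no transmission role and the direction of spread can be misread

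*Combined protocol and SAP*

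**What the plan says.** The Infected model section under Statistical Methods sets four definitions and does not separate them by pathogen.

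- Index case: "The index cases are the first members of the household to have clinically apparent illness confirmed by laboratory studies".
- Source: "Identified source of infection within the household is defined as the first case in the household who displayed clinically apparent disease". A second condition is joined to the first: the person must be someone "who have clear contact history with individuals outside the household who had illnesses suggestive of" either infection.
- Secondary case: "The secondary cases are defined as other family members whose respiratory symptoms occurred later than the index cases' illness".
- Transmission interval: the time from disease onset in the household's first case to disease onset in a secondary case.

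On natural history, Background & Rationale says "Asymptomatic carriage of *S. pneumoniae* in the nasopharynx is a prerequisite for disease". Significance states the aim of establishing household transmission, particularly in the elderly and in infants and children.

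On sampling, Study design provides that when a member has suspected pneumonia, "Family members in the same household will be asked to undergo screening with a nasopharyngeal or throat swab and urine sample". Pneumococcal serotyping is also planned. In the data and specimen table, family specimens appear only in the row for lower respiratory illness, and the enrollment row lists no specimen.

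**The concern.** If carriage comes before disease and is silent, the first person to fall ill need not be the first to have acquired the organism. A rule based on illness order may be workable for RSV, about which the plan makes no comparable statement on silent carriage. For pneumococcus it conflicts with the plan's own account.

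Two kinds of error follow. A carrier who stays well can never be named as the source, and a member who acquires the organism without symptoms is never counted as a secondary case. Both bear on the aim of describing who transmits to whom between the elderly and young children. The study collects family swabs and serotypes that could inform this, but the definitions give a symptom-free positive result no place.

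**Working it through.** The plan states no figure on this point, so the check is mainly textual.

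**Step 1. Is illness a necessary condition for each role?**

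| Role | Condition | Open to a symptom-free carrier? |
|---|---|---|
| Index case | First clinically apparent illness, laboratory confirmed | No |
| Source | First clinically apparent disease, and ill contacts outside the household | No |
| Secondary case | Respiratory symptoms later than the index illness | No |
| Transmission interval | Disease onset to disease onset | Neither end can be a silent acquisition |

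**Step 2. Apply the rule to pneumococcal examples.** Suppose a baby develops laboratory-confirmed pneumonia, and the family screen finds a grandparent carrying the same serotype.

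- The grandparent stays well and the baby had contact with an ill outsider. The baby is index case and source. The grandparent has no role.
- The grandparent stays well and the baby had no such contact. The household has no identified source, although a carrier of the matching serotype is present.
- The grandparent was the earlier carrier but develops symptoms after the baby. The grandparent becomes a secondary case, the interval runs from baby to grandparent, and the direction is reversed.
- The grandparent acquired the organism from the baby and stays well. A true household acquisition is not counted.

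**Step 3. Does another analysis repair this?** A symptom-free positive swab can enter three places:

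- the susceptible-infected-susceptible model, where a carrier counts as infected whether or not ill;
- the three-level mixed model of infection status;
- the isolation-rate endpoint.

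None of the three names a source, and the plan links none of them to the definitions above.

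**Step 4. How common might a silent carrier be? (Illustration only.)** Let c be the chance that any one member carries pneumococcus, and k the number of other members when the first falls ill. Assuming independence, P(at least one other carrier) = 1 − (1 − c)^k.

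Inputs: k = 2 is a couple and baby, with one of the three ill. k = 5 is a couple, baby, one child and two grandparents; the counts of one child and two grandparents are assumed, because the plan fixes neither. The values c = 10% and 30% are assumed. The 65.8% is the oropharyngeal figure cited in Background & Rationale, which does not state the population behind it.

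| c | k = 2 | k = 5 |
|---|---|---|
| 10% | 1 − 0.90² = 19% | 1 − 0.90⁵ = 41% |
| 30% | 1 − 0.70² = 51% | 1 − 0.70⁵ = 83% |
| 65.8% | 1 − 0.342² = 88% | 1 − 0.342⁵ = 99.5% |

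These figures show how often some other carrier would be present, and that this is more frequent in larger households. They do not show how often a source is wrong. That also depends on serotype match, the outside-contact condition, clustering of carriage within households, and whether a true source has already cleared.

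**The case against.** The best defence is that carriage is not ignored. The susceptible-infected-susceptible model estimates acquisition and clearance from carrier status with no illness requirement, the mixed model follows infection status within person and household, and the primary endpoint is isolation rates. The source label is not an endpoint, and no named model or test uses it. The outside-contact condition also stops the first ill member from automatically becoming the source. All of this stands and limits the reach of the point. It does not supply a valid source or interval for pneumococcus.

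A reader might infer that a silent carrier's swab is lost to the transmission analysis altogether. The documents do not support that: the swab is lost only to the labelling of roles and intervals.

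A reader might also infer that the rule makes it impossible to support the plan's idea about the elderly: "The elderly might colonize with *S. pneumoniae* first and then get the RSV acquisition from the younger households". It does not. The order described is within one person, pneumococcus before RSV. It does not say that the elderly are the first carriers in the household or the pneumococcal source. Testing it needs a pneumococcal result that precedes that person's RSV episode, and the source label plays no part.

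A further fair objection is that sampling is the tighter limit. Specimens follow illness, so carriage before the first illness is mostly unobserved, and rewording cannot recover it. That stands, and it is a reason not to assert a direction.

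**Conclusion.** The point holds for *S. pneumoniae*. As written, the definitions exclude symptom-free carriers from every transmission role, and they treat order of illness as order of acquisition against the plan's own account of carriage. The source label and the transmission interval can therefore be wrong in direction, and silent acquisitions go uncounted. This follows from the text and needs no assumption about prevalence.

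The size of the error is not known. The carriage percentages depend on assumed prevalence, household size and independence, and should not be read as upper bounds on the share of wrong sources. They suggest only that a silent carrier is a plausible candidate source, more often in extended families. That matters if sources or intervals are compared between family types.

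The definitions should be amended before sources are classified. The primary endpoint is unaffected. No change is needed to symptom ordering for RSV, and its outside-contact condition may stay.

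**What to change.** Replace the single set of definitions in the Infected model section with one set per pathogen.

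1. **RSV:** keep symptom-onset order among laboratory-confirmed cases.
2. ***S. pneumoniae*, clusters:** define a household cluster by matching serotype, and count symptom-free screening positives as members.
3. ***S. pneumoniae*, direction:** assign a source and an interval only where an earlier specimen shows the order, for example one member positive for the serotype when the other tested negative. Otherwise report the cluster as 'direction undetermined'.
4. ***S. pneumoniae*, outside contact:** record contact with ill outsiders as a descriptor, not as a condition for being the source.
5. **Pneumococcus before RSV in the elderly:** report this only from members with a pneumococcal result that predates their RSV episode, and give the number who qualify.
6. **Link to the model:** state that the susceptible-infected-susceptible model estimates acquisition and clearance and does not assign sources.

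The cost is definition wording; the swabs and serotyping are already planned. The drawback is that, with specimens collected only after illness, most pneumococcal clusters will probably be reported with undetermined direction. The change mainly removes unsupported claims of direction and does not by itself supply supported ones.
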